11.0 Tumor Response Evaluation Criteria

11.1 Evaluation of Target Lesions

This section provides the definitions of the criteria used to determine objective tumor response for target lesions.

- Complete response (CR): disappearance of all target lesions
Any pathological lymph nodes (whether target or non-target) must have reduction in short axis to < 10 mm.
- Partial response (PR): at least a 30% decrease in the sum of diameters of target lesions, taking as reference the baseline sum of diameters
- Progressive disease (PD): at least a 20% increase in the sum of diameters of target lesions, taking as reference the smallest sum on study (nadir), including baseline
In addition to the relative increase of 20%, the sum must also demonstrate an absolute increase of at least 5 mm.
The appearance of one or more new lesions is also considered progression.
- Stable disease (SD): neither sufficient shrinkage to qualify for PR nor sufficient increase to qualify for PD, taking as reference the smallest sum on study

11.2 Evaluation of Non-Target Lesions

This section provides the definitions of the criteria used to determine the tumor response for the group of non-target lesions. While some non-target lesions may actually be measurable, they need not be measured and, instead, should be assessed only qualitatively at the time points specified in the protocol.

- CR: disappearance of all non-target lesions and (if applicable) normalization of tumor marker level)
All lymph nodes must be non-pathological in size (< 10 mm short axis).
- Non-CR/Non-PD: persistence of one or more non-target lesion(s) and/or (if applicable) maintenance of tumor marker level above the normal limits
- PD: unequivocal the appearance of one or more new lesions is also considered progression.

12.0 Safety Monitoring and Reporting

All study patients who have received neratinib and capmatinib as combination therapy will be evaluable for safety. The ongoing review of safety data will include review of clinical AEs and SAEs.

12.1 Adverse Event

12.1.1 Adverse Event Definition

An Adverse Event is defined as any untoward medical occurrence in a patient regardless of its causal relationship to study treatment. An AE can be any unfavorable and unintended sign

(including any clinically significant abnormal laboratory test result), symptom, or disease temporally associated with the use of the study treatment, whether or not it is considered to be study drug(s) related. Included in this definition are any newly occurring events and any previous condition that has increased in severity or frequency since the administration of study

12.1.2 Adverse Event Attribution

Attribution is the determination of whether an adverse event is related to a medical treatment or procedure.

Definite - the adverse event is clearly related to the investigational agent(s).

Probable - the adverse event is likely related to the investigational agent(s).

Possible - the adverse event may be related to the investigational agent(s).

Unlikely - The adverse event is doubtfully related to the investigational agent(s).

Unrelated - The adverse event is clearly NOT related to the investigational agent(s).

The Study PI or designee will be responsible for assigning attribution of adverse events to the study agent and signing the case report form.

12.1.3 Adverse Event Severity

The severity of the adverse events (AEs) will be graded according to the National Cancer Institute Common Terminology Criteria for Adverse Events (NCI CTCAE) 5.0. Events not included in the NCI CTCAE will be scored as follows:

General grading:

Grade 1: Mild: discomfort present with no disruption of daily activity, no treatment required beyond prophylaxis.

Grade 2: Moderate: discomfort present with some disruption of daily activity, require treatment.

Grade 3: Severe: discomfort that interrupts normal daily activity, not responding to first line treatment.

Grade 4: Life Threatening: discomfort that represents immediate risk of death

Grade 5: Fatal

12.1.4 Adverse Event Recording

Adverse events and Serious Adverse Events will be captured in the study database REDCap.

All AEs and SAEs will be captured during the study Phase 1b portion. For the Phase II portion of the study, only AEs \geq grade 2 non-hematological and \geq grade 3 hematological AEs, occurring after first protocol intervention observed by the investigator or reported by the subject (whether or not attributed to investigational product), will be documented in the medical record and recorded in RedCap. Baseline toxicities will be documented in the patients' medical record.

Abnormal laboratory values will not be reported as AEs; however, the abnormal laboratory value is considered to be an AE if the abnormality:

- Results in discontinuation from the study
- Requires treatment, modification/interruption of study treatment dose, or any other therapeutic intervention
- Is judged to be of significant clinical importance
- If a laboratory abnormality is one component of a diagnosis or syndrome, then only the diagnosis or syndrome should be recorded on the AE page of the eCRF. If the abnormality was not a part of a diagnosis or syndrome, then the laboratory abnormality should be recorded as the AE.

12.2 Serious Adverse Event Reporting (SAE)

12.2.1 Internal SAE reporting to Investigational New Drug (IND) Office

Serious Adverse Event (SAE) Reporting Requirements for M D Anderson Sponsor Single Site IND Protocols

An adverse event or suspected adverse reaction is considered “serious” if, in the view of either the investigator or the sponsor, it results in any of the following outcomes:

- Death
- A life-threatening adverse event
- Inpatient hospitalization or prolongation of existing hospitalization
- A persistent or significant incapacity or substantial disruption of the ability to conduct normal life functions.
- A congenital anomaly/birth defect.

Important medical events that may not result in death, be life-threatening, or require hospitalization may be considered a serious adverse drug experience when, based upon appropriate medical judgment, they may jeopardize the patient or subject and may require medical or surgical intervention to prevent one of the outcomes listed in this definition.

Examples of such medical events include allergic bronchospasm requiring intensive treatment in an emergency room or at home, blood dyscrasias or convulsions that do not result in inpatient hospitalization, or the development of drug dependency or drug abuse (21 CFR 312.32).

- Important medical events as defined above, may also be considered serious adverse events. Any important medical event can and should be reported as an SAE if deemed appropriate by the Principal Investigator or the IND Sponsor, IND Office.
- All events occurring during the conduct of a protocol and meeting the definition of a SAE must be reported to the IRB in accordance with the timeframes and procedures outlined in “The University of Texas M. D. Anderson Cancer Center Institutional Review Board Policy on Reporting Adverse Events for Drugs and Devices”.

- Serious adverse events will be captured from the time of the first protocol-specific intervention, until 30 days after the last dose, unless the participant withdraws consent.
- Serious adverse events must be followed until clinical recovery is complete and laboratory tests have returned to baseline, progression of the event has stabilized, or there has been acceptable resolution of the event.
- All SAEs, expected or unexpected/ initial or follow up, must be reported to the IND Office **within 5 working days of knowledge of the event** regardless of the attribution.
- Death or life-threatening events that are unexpected, possibly, probably or definitely related to drug must be reported (initial or follow up) to the IND Office **within 24 hours of knowledge of the event**
- Additionally, any serious adverse events that occur after the 30-day time period that are related to the study treatment must be reported to the IND Office. This may include the development of a secondary malignancy.
- The electronic SAE application (eSAE) will be utilized for safety reporting to the IND Office and MD Anderson IRB.
- All events reported to the supporting company must also be reported to the IND Office

Reporting to FDA:

- Serious adverse events will be forwarded to FDA by the IND Sponsor according to 21 CFR 312.32.

It is the responsibility of the PI and the research team to ensure serious adverse events are reported according to the Code of Federal Regulations, Good Clinical Practices, the protocol guidelines, the sponsor's guidelines, and Institutional Review Board policy.

12.2.3 Investigator Communication with Supporting Company

The MDACC Internal SAE Report Form will be used for reporting to Puma Biotechnology Inc. and Novartis and reporting timeline is as below:

- Death that is unanticipated and definitely, probably or possibly related to study intervention that occur any time from the first protocol-specific intervention, until 30-days after the last day of active study intervention will be reported to Puma Biotechnology Inc. and Novartis within 24 working hours, not including holidays.
- All other SAEs regardless of suspected causality (unanticipated, and definitely, probably or possibly related to study drugs) will be reported to Puma Biotechnology Inc. and Novartis within 24 working hours, not including holidays. The investigator must assess and record the relationship of each SAE to each specific study treatment (if there is more than one study treatment), and submit the completed form to Puma via email to [contact] and to Novartis via email to [contact] (Fax: [name]).

- Any additional information for the SAE including complications, progression of the initial SAE, and recurrent episodes must be reported as follow-up to the original episode within 24 hours of the investigator receiving the follow-up information. An SAE occurring at a different time interval or otherwise considered completely unrelated to a previously reported one should be reported separately as a new event.
- Any SAEs experienced after the 30-day safety follow-up period should only be reported to Novartis if the investigator suspects a causal relationship to the study treatment.
- Follow-up information is submitted in the same way as the original SAE Report. Each re-occurrence, complication, or progression of the original event should be reported as a follow-up to that event regardless of when it occurs. The follow-up information should describe whether the event has resolved or continues, if and how it was treated, whether the blind was broken or not, and whether the subject continued or withdrew from study participation.
- If the SAE is not previously documented in the Investigator's Brochure or Package Insert (new occurrence) and is thought to be related to the Novartis study treatment, an oncology Novartis Chief Medical Office and Patient Safety (CMO&PS) department associate may urgently require further information from the investigator for Health Authority reporting. Novartis may need to issue an Investigator Notification (IN), to inform all investigators involved in any study with the same drug that this SAE has been reported. Suspected Unexpected Serious Adverse Reactions (SUSARs) will be collected and reported to the competent authorities and relevant ethics committees in accordance with Directive 2001/20/EC or as per national regulatory requirements in participating countries.
- Other events requiring reporting - Pregnancy

To ensure subject safety, each pregnancy occurring while the subject is on study treatment must be reported to Novartis within 24 hours of learning of its occurrence. The pregnancy should be followed up to determine outcome, including spontaneous or voluntary termination, details of the birth, and the presence or absence of any birth defects, congenital abnormalities, or maternal and/or newborn complications.

13.0 Statistical Consideration

Safety will be evaluated in this study through the monitoring of adverse events and serious adverse events defined as Section 12.1. This is an IND study and will be monitored by MD Anderson IND office.

13.1 Phase 1b Dose-Finding Design

We will employ the Bayesian optimal interval (BOIN) design (Liu and Yuan, 2015; Yuan et al., 2016) (24, 25), with the 3+3 design run-in, to find the MTD (see Appendix 1 for design parameters). The BOIN design is implemented in a simple way similar to the traditional 3+3 design, but is more flexible and possesses superior operating characteristics that are comparable to those of the more complex model-based designs, such as the continual reassessment method (CRM) (Zhou et al., 2018)(26).

The target toxicity rate for the MTD is $\phi = 0.25$ and the maximum sample size for dose escalation is 18. We will enroll and treat patients in cohorts of size 3. DLTs are defined in **Section 7.4** and only those DLTs that occur within **the first 2 cycles (56 days)** will be used for dose finding. As shown in Figure 2, the Boin design uses the following rule, optimized to minimize the probability of incorrect dose assignment, to guide dose escalation/de-escalation:

- if the observed DLT rate at the current dose is ≤ 0.197 , escalate the dose to the next higher dose level;
- if the observed DLT rate at the current dose is > 0.298 , de-escalate the dose to the next lower dose level;
- otherwise, stay at the current dose.

The 3+3 design run-in will be applied to override the above decision rule when the number of patients treated at the current dose is 3. That is, we will escalate the dose if 0/3 DLT, stay at the current dose if 1/3 DLT, and de-escalate the dose if $\geq 2/3$ DLTs. For the purpose of overdose control, doses j and higher levels will be eliminated from further examination if $\Pr(p_j > 0.25 | \text{data}) > 0.95$ and at least 3 evaluable patients have been treated at dose level j , where p_j is the true DLT rate of dose level $j, j = 1, \dots, 3$. This posterior probability is evaluated based on the beta-binomial model $y_j | p_j \sim \text{binomial}(p_j)$ with $p_j \sim \text{uniform}(0,1)$, where y_j is the number of patients experienced DLT at dose level j . When the lowest dose is eliminated, stop the trial for safety. The probability cutoff 0.95 is chosen to be consistent with the common practice that when the target DLT rate $\leq 1/6$, a dose with 2/3 patients experienced DLT is eliminated. The above dose escalation/de-escalation and elimination rule can be equivalently presented in Table 18, which will be used to conduct the trial.

The steps to implement the Boin design are described as follows:

1. Patients in the first cohort are treated at dose level 1.
2. To assign a dose to the next cohort of patients, conduct dose escalation/de-escalation according to the rule displayed in Table 18. When using Table 18, please note the following:
 - a. “Eliminate” means eliminate the current and higher doses from the trial to prevent treating any future patients at these doses because they are overly toxic.
 - b. When we eliminate a dose, automatically de-escalate the dose to the next lower level. When the lowest dose is eliminated, stop the trial for safety. In this case, no dose should be selected as the MTD.
 - c. If none of the actions (i.e., escalation, de-escalation or elimination) is triggered, treat the new patients at the current dose.
 - d. If the current dose is the lowest dose and the rule indicates dose de-escalation, treat the new patients at the lowest dose unless the number of DLTs reaches the elimination boundary, at which point terminate the trial for safety.

[figure not shown]
e. If the current dose is the highest dose and the rule indicates dose escalation, treat the new patients at the highest dose.

3. Repeat step 2 until the maximum sample size of 18 is reached, or stop the trial if the number of evaluable patients treated at the current dose reaches 9.

Table 18. Dose Escalation/Deescalation Rule for the BOIN Design

Number of evaluable patients treated at current dose												
	1	2	3	4	5	6	7	8	9	10	11	12
Escalate if # of DLT <=	0	0	0	0	0	1	1	1	1	1	2	2
Deescalate if # of DLT >=	1	1	2*	2	2	2	3	3	3	3	4	4
Eliminate if # of DLT >=	NA	NA	3	3	3	4	4	4	5	5	6	6

Note. "# of DLT" is the number of patients with at least 1 DLT. When none of the actions (i.e., escalate, de-escalate or eliminate) is triggered, stay at the current dose for treating the next cohort of patients. "NA" means that a dose cannot be eliminated before treating 3 evaluable patients. "*" indicates the 3+3 design run-in.

$$* \text{ DLT rate} = \frac{\text{Total number of patients who experienced DLT at the current dose}}{\text{Total number of evaluable patients treated at the current dose}}$$

Figure 2. Flowchart for trial conduct using the BOIN design

After the trial is completed, select the MTD based on isotonic regression as specified in Liu and Yuan (2015) (24). This computation is implemented by the shiny app “BOIN” (Zhou et al., 2020) (27) available at <http://www.trialdesign.org>. Specifically, select as the MTD the dose for which the isotonic estimate of the toxicity rate is closest to the target toxicity rate. If there are ties, select the higher dose level when the isotonic estimate is lower than the target toxicity rate and select the lower dose level when the isotonic estimate is greater than or equal to the target toxicity rate.

Operating Characteristics

Table 19 shows the operating characteristics of the trial design based on 1000 simulations of the trial using shiny app “BOIN” (BOIN V2.6.3.0) available at <http://www.trialdesign.org>. The operating characteristics show that the design selects the true MTD, if any, with high probability and allocates more patients to the dose levels with the DLT rate closest to the target of 0.25.

Table 19. Operating Characteristics of the BOIN Design

	Dose Level -2	Dose Level -1	Dose Level 1	Dose Level 2	Dose Level 3	Number of Patients	% Early Stopping
Scenario 1							
True DLT Rate	0.25	0.41	0.45	0.49	0.53		
Selection %	50.1	29	13.2	2.4	0.7		4.6
% Pts Treated	24.7	32.2	34	7.6	1.4	17.2	
Scenario 2							
True DLT Rate	0.12	0.25	0.42	0.49	0.55		
Selection %	19	52.1	24.1	4	0.6		0.2
% Pts Treated	12.2	35.7	41.4	9.2	1.5	17.1	
Scenario 3							
True DLT Rate	0.04	0.12	0.25	0.43	0.63		
Selection %	0.7	18.4	62.8	17.4	0.7		0
% Pts Treated	1.7	19	50.6	24.6	4	16.6	
Scenario 4							
True DLT Rate	0.02	0.06	0.1	0.25	0.4		
Selection %	0	0.5	25.3	54.2	20		0
% Pts Treated	0	2.6	35.9	39.2	22.2	17.1	

Note: “% Early Stopping” refers to early stopping due to excessive DLT.

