4.1 Phase 1b – Dose Escalation of Neratinib with Capmatinib

This phase of the study will employ the Bayesian optimal interval (BOIN) design (Liu and Yuan, 2015 Yuan et al., 2016) (24, 25), with the 3+3 design run-in, to find the MTD. The BOIN design is implemented in a simple way similar to the traditional 3+3 design, but is more flexible and possesses superior operating characteristics that are comparable to those of the more complex model-based designs, such as the continual reassessment method (CRM) (Zhou et al., 2018) (26). The maximum sample size for dose escalation is 18. Patients are treated in cohorts of 3, beginning with Neratinib PO dose level 1 (120 mg, Dose 1-7, 160 mg, through end of treatment, see Table 2) in combination with Capmatinib PO level 1 (400 mg, see Table 3), with a maximum of 12 patients per dose. The target toxicity rate for the maximum tolerable dose (MTD) is 25%.

This trial was designed and will be conducted using the shiny app “BOIN” (BOIN V2.6.3.0) available at <http://www.trialdesign.org..> Further information about the design can be found in Section 13.

Table 2. Phase Ib Neratinib PO dose levels, in combination of Capmatinib PO.

Dose Level	1	2	3
Neratinib PO	120 mg, Dose 1-7, 160 mg, through end	120 mg, Dose 1-7, 160 mg, Dose 8-14, 200 mg, through end	120 mg, Dose 1-7, 160 mg, Dose 8-14, 240 mg, through end
Capmatinib PO	400 mg b.i.d.	400 mg b.i.d.	400 mg b.i.d.

Table 3 : Fallback Dose levels.

	Dose level -1	Dose level -2
Neratinib PO	120 mg, Dose 1-7, 160 mg, through end	120 mg, Dose 1-7, through end
Capmatinib PO	300 mg b.i.d.	200 mg b.i.d.

Note: dose reduction should be based on the worst toxicity demonstrated at the last dose.

Dose reduction below 200 mg is not allowed

This protocol will be monitored by IND Office and safety data will be reviewed by IND Office after all subjects in a given cohort have completed the DLT assessment period (Cycle 1 and 2, total 56 days) and the dose level for next cohort will be determined based on the results.

Prior to advancing/changing dose levels, a cohort summary will be completed and submitted to the IND Medical Monitor for review and approval.

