Appendix 1: Phase Ib Trial and Design Specifications

Parameter	Value
Number of doses	5
Starting dose	3
Max sample size	18
Cohort size	3
Stop trial if # patients assigned to single dose reaches	9
Apply the 3+3 design run-in	TRUE
Use accelerated titration	FALSE
Target toxicity probability	0.25
Use the default alternatives to minimize decision errors	TRUE
Alternative (unacceptable high toxicity) for optimization	Default
Alternative (unacceptable low toxicity) for optimization	Default
Eliminate dose threshold	0.95
Impose a more stringent safety stopping rule	FALSE
Require the isotonic estimate of the DLT probability for the dose selected as the MTD less than the de-escalation boundary	FALSE
Number of repetitions per scenario	1000
Random number generator seed	6

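### The phase Ib stop-at-9 rule as written in Section 13.1 did not produce Table 19; applied literally, it selects an over-toxic dose more often than the table reports in scenarios 1 and 2

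*Combined protocol and SAP*

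**What the plan says.** Section 13.1, step 3, continues dose finding to 18 patients, or ends it earlier: "stop the trial if the number of evaluable patients treated at the current dose reaches 9". Appendix 1 lists the software setting "Stop trial if # patients assigned to single dose reaches" with the value 9. Neither place says whether the stop depends on the next dose decision.

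The Synopsis and Section 4.1 instead describe cohorts of 3 "with a maximum of 12 patients per dose", and Table 18 has decision columns up to 12 evaluable patients.

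Step 2 settles two boundary cases by repeating the same dose. At the bottom of the range: "treat the new patients at the lowest dose unless the number of DLTs reaches the elimination boundary". At the top: "If the current dose is the highest dose and the rule indicates dose escalation, treat the new patients at the highest dose".

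The evidence for the design is Table 19, "based on 1000 simulations of the trial using shiny app". On conduct, Section 13.1 refers to "Table 18, which will be used to conduct the trial", while Section 4.1 says "This trial was designed and will be conducted using the shiny app".

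**The concern.** With cohorts of 3, a plain stop at 9 means that no dose can ever hold 12 patients, so the 12-per-dose text and the last columns of Table 18 have no use. That suggests the simulation used a different rule from the one printed.

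The difference matters because the trial starts at the third of five doses. If the starting dose is too toxic, a plain stop at 9 can end dose finding at a dose that Table 18 says to leave, and the isotonic step may then choose that dose as the MTD. Table 19 is the plan's evidence that the rule finds the MTD reliably, and that MTD is the phase II dose.

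**Working it through.** **Inputs** (Section 13.1 and Appendix 1): five doses, start at the third; cohorts of 3; maximum 18; escalate at a DLT rate ≤ 0.197, de-escalate at > 0.298; 3+3 run-in at n = 3; eliminate if Pr(p > 0.25 | data) > 0.95 under a uniform prior with n ≥ 3; MTD by isotonic regression; true DLT rates from Table 19. One assumption is not in the documents: pseudo-counts of 0.05 events per 0.1 patients in the isotonic step. Leaving them out changes selection by at most 0.1 point.

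**Boundaries.** All 12 columns of Table 18 reproduce. For example, 3/3 gives Pr = 1 − 0.25⁴ = 0.996 (eliminate), and 2/3 gives 1 − (4·0.25³ − 3·0.25⁴) = 0.949 (do not eliminate).

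**One path by hand.** Level 1 has 1/3 (stay), then 2/6 (de-escalate). Level −1 has 0/3 (escalate). Level 1 then reaches 4/9. Table 18 says de-escalate (3 or more) but not eliminate (5 or more). Literal step 3 ends the trial at 12 of 18 patients. The raw rates are 0/3 = 0 and 4/9 = 0.444; their distances from 0.25 are 0.250 and 0.194, so level 1 becomes the MTD with six places unused.

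**Full check.** All paths were enumerated exactly, so these results carry no simulation error. Table 19 rests on 1000 runs, so its standard error (SE) is the exact SD of N, or the binomial SD, divided by √1000. For N under the literal rule the SE is about 0.06 to 0.07. Gaps are Table 19 minus exact, from unrounded values.

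| Mean N, by stopping rule | Sc. 1 | Sc. 2 | Sc. 3 | Sc. 4 | Largest n on a dose |
|---|---|---|---|---|---|
| Table 19 | 17.2 | 17.1 | 16.6 | 17.1 | – |
| (a) Literal: stop at 9 | 16.10 | 15.30 | 14.76 | 15.97 | 9 |
| gap in SE | 16.0 | 25.9 | 28.5 | 18.6 | |
| (b) Stop at 9 if the next cohort goes to the same dose | 17.18 | 16.99 | 16.63 | 17.06 | 12 |
| gap in SE | 0.5 | 1.9 | −0.4 | 0.8 | |
| (c) Stop if the newly assigned dose already has 9 | 17.07 | 16.71 | 16.23 | 16.94 | 9 |
| gap in SE | 2.5 | 6.5 | 5.5 | 2.8 | |
| (d) Stop at 9 only if Table 18 triggers no action | 17.43 | 17.33 | 17.02 | 17.30 | 15 |
| gap in SE | −4.8 | −4.7 | −7.0 | −4.1 | |

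Rule (b) includes steps 2d and 2e and the case where the next higher dose has been eliminated. Under it a dose reaches 12 patients in 3.7/9.2/13.1/3.7% of trials and never more.

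**Selection of a dose with true DLT rate above 0.25.** The Table 19 figures are sums of its cells, e.g. scenario 1: 29 + 13.2 + 2.4 + 0.7 = 45.3.

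| | Sc. 1 | Sc. 2 | Sc. 3 | Sc. 4 |
|---|---|---|---|---|
| Table 19 | 45.3% | 28.7% | 18.1% | 20.0% |
| (a) Literal | 51.7% | 38.0% | 20.0% | 20.0% |
| distance from Table 19, in SE | 4.1 | 6.0 | 1.5 | 0.0 |
| (b) Same dose | 46.0% | 29.3% | 19.0% | 19.2% |

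Under (a), the true MTD is selected in 44.6% and 46.9% of trials in scenarios 1 and 2, against 50.1% and 52.1% in Table 19. The starting dose (true DLT rates 0.45 and 0.42) is selected in 20.2% and 33.1%, against 13.2% and 24.1%.

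**Mechanism.** Rule (a) ends the trial before 18 patients while Table 18 calls for a lower dose in 25.6/38.4/36.6/18.0% of trials. In scenarios 1 and 2 that same over-toxic dose is then selected in 16.5% and 17.8% of all trials.

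**The case against.** The strongest reply is that nothing is wrong with Table 19: rule (b) reproduces it, so the defect is one missing clause. That is right as far as it goes, but the clause appears in neither step 3 nor Appendix 1.

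Next, step 3 follows a step that assigns the next dose, so the current dose could mean the newly assigned one, rule (c). Over-toxic selection is then 46.1% and 29.9% in scenarios 1 and 2, and the safety difference disappears. The misfit in N is only 0.1 to 0.4 patients. Table 19 rounds N to one decimal; allowing 0.05 for that lowers the gaps to 1.5/5.7/4.7/1.9 SE. So scenarios 1 and 4 do not exclude this reading, but scenarios 2 and 3 still do, and it too caps each dose at 9.

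Third, conduct in the app should follow whatever was simulated. Section 4.1 requires medical monitor approval of dose changes. Section 13.2 requires IND Sponsor approval before phase II, adds toxicity monitoring there, and allows a lower dose for ER+ patients. These protections are real and reduce the consequence. They do not remove the conflict, because Section 13.1 also says that Table 18 governs conduct.

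Finally, Figure 2, the conduct flowchart, was not available and may state the condition. Rule (b) is also inferred from the fit to one set of 1000 runs, where the largest selection discrepancy is 2.0 SE (correct selection in scenario 3, 59.7% against 62.8%). Both limits stand, so the app settings must be checked before any wording is fixed.

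**Conclusion.** The concern holds. Neither reading of step 3 as written gives Table 19, and both conflict with the 12-per-dose text. Read literally, the rule raises over-toxic selection by 6.4 points in scenario 1 (51.7 − 45.3) and 9.3 points in scenario 2 (38.0 − 28.7), and lowers correct selection by 5.5 and 5.2 points. Scenarios 3 and 4 are not materially affected beyond a mean N that is 1.8 and 1.1 patients lower. Under the newly-assigned-dose reading only the small gap in N remains.

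The result rests on the stated design settings and the isotonic pseudo-count assumption, which has almost no influence. That the simulation used the same-dose condition is a well-supported inference, not something the documents state. The point should be corrected; it does not undermine the design itself.

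**What to change.** Reconcile step 3, Appendix 1, the 12-per-dose text and Table 19 in one of two ways.

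1. Check the app settings. If they confirm the condition, add to step 3 the clause *and the next cohort would be assigned to the same dose*, and refer to it in Appendix 1. A shorter clause such as *and Table 18 says stay* should not be used. It ignores steps 2d and 2e and eliminated higher doses, overshoots Table 19 by 4.1 to 7.0 SE (rule (d)), and lets a dose reach 15 patients in 0.7/2.4/3.2/1.3% of trials.
2. Keep the literal rule, re-run Table 19 under it, replace its figures, and align the 12-per-dose text in the Synopsis and Section 4.1.

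If Figure 2 states a condition, step 3 should match it. The cost is one clause and a cross-reference, or one simulation re-run and text corrections in two places. Neither needs patients beyond the maximum of 18.
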